11.2 Monitoring for Adverse Events

At each visit, after the subject has had the opportunity to spontaneously mention any problems, the investigator should inquire about AEs by asking the standard questions shown below and report as applicable:

- “Have you had any health problems since your last study visit?”

[figure not shown]
- “Have there been any changes in the medicines you take since your last study visit?”

In addition, changes in any *protocol-specific parameters* [REDACTED] evaluated during the study are to be reviewed by the investigator. Any untoward (unfavorable and unintended) change in a *protocol-specific parameter* [REDACTED] that is clinically relevant, in the opinion of the investigator, is to be reported as an AE. These clinically relevant changes will be reported regardless of causality.

11.3 Procedures for Recording and Reporting

AEs are collected from the time of informed consent. Any pre-existing medical conditions or signs/symptoms present in a subject prior to the start of the study (i.e., before informed consent is signed) are not considered AEs in the study and should be recorded in the Medical History section of the eCRF.

In addition, temporary lens awareness or visual changes during the fitting process are not considered AEs if the investigator assesses that the symptom(s) can reasonably resolve within the anticipated adaptation period.

For each recorded event, the ADEs and SAEs documentation must include: date of occurrence, severity, treatment (if applicable), outcome, and assessments of the seriousness and causality. In addition, the investigator must document all device deficiencies reported or observed with test and comparator products on the Device Deficiency eCRF. The site must submit all available information on ADEs, SAEs, and device deficiencies to the study sponsor immediately as follows:

- All SAEs must be reported immediately (within 24 hours) of the Investigator’s or site’s awareness.
- ADEs that do not meet seriousness criteria and device deficiencies must be reported within 10 calendar days of the Investigator’s or site’s awareness.
- A printed copy of the completed Serious Adverse Event and Adverse Device Effect and/or Device Deficiency eCRF must be included with product returns. Additional relevant

information after initial reporting must be entered into the eCRF as soon as the data become available.

- Document any changes to concomitant medications on the source.
- Document all relevant information from Discharge Summary, Autopsy Report,
- Certificate of Death etc., if applicable, in narrative section of the *Serious Adverse Event and Adverse Device Effect eCRF*.

Note: Should the EDC system become non-operational, the site must complete the appropriate paper *Serious Adverse Event and Adverse Device Effect and/or Device Deficiency* Form. The completed form is emailed to the study sponsor at [contact] according to the timelines outlined above; however, the reported information must be entered into the EDC system once it becomes operational.

Any AEs and device deficiencies for non-study marketed devices/products (i.e., AOSEPT PLUS with HydraGlyde Cleaning & Disinfecting Solution) will be considered and processed as spontaneous (following the post-market vigilance procedures) and should be communicated to the device's/product's manufacturer as per local requirements.

Study sponsor representatives may be contacted for any protocol related question and their contact information is provided in the Manual of Procedures that accompanies this protocol.

Further, depending upon the nature of the AE or device deficiency being reported, the study sponsor may request copies of applicable portions of the subject's medical records. The investigator must also report all AEs and device deficiencies that could have led to a SADE according to the requirements of regulatory authorities or IRB/IEC.

Intensity and Causality Assessments

Where appropriate, the investigator must assess the intensity (severity) of the AE based on medical judgment with consideration of any subjective symptom(s), as defined below:

Intensity (Severity)

Mild An AE is mild if the subject is aware of but can easily tolerate the sign or symptom.

Moderate An AE is moderate if the sign or symptom results in discomfort significant enough to cause interference with the subject's usual activities.

Severe An AE is severe if the sign or symptom is incapacitating and results in the subject's inability to work or engage in their usual activities.

For every AE in the study, the investigator must assess the causality (Related or Not Related to the medical device or study procedure). An assessment of causality will also be performed by study sponsor utilizing the same definitions, as shown below:

Causality

Related An AE classified as related may be either definitely related or possibly related where a direct cause and effect relationship with the medical device or study procedure has not been demonstrated, but there is a reasonable possibility that the AE was caused by the medical device or study procedure.

Not Related An AE classified as not related may either be definitely unrelated or simply unlikely to be related (i.e., there are other more likely causes for the AE).

The study sponsor will assess the AEs and may upgrade the investigator's assessment of seriousness and/or causality. The study sponsor will notify the investigator of any AEs that is upgraded from non-serious to serious or from unrelated to related.

11.4 Return product analysis, if applicable

Study sponsor representatives and their contact information are provided in the MOP that accompanies this protocol.

Alcon products associated with device deficiencies and/or product related AEs should be returned and must include the Complaint # which will be provided by study sponsor after the case is entered in the study sponsor's Global Product Complaint Management System (GPCMS).

11.5 Unmasking of the Study Treatment

Investigators are unmasked in this study. However, the identity of the assigned medical device should not be disclosed to subjects who are masked during the study. The Study Sponsor must be informed of all cases in which unmasking of the subject(s) has occurred and of the circumstances involved. The Study Sponsor should be informed in advance of unmasking when possible, except in the event of a medical emergency. Additionally, the

Study Sponsor may be required to unmask the information in order to fulfill expedited regulatory reporting requirements.

11.6 Follow-Up of Subjects with Adverse Events

The investigator is responsible for adequate and safe medical care of subjects during the study and for ensuring that appropriate medical care and relevant follow-up procedures are maintained after the study.

The investigator should provide the study sponsor with any new safety information (which includes new AEs and changes to previously reported AEs) that may affect the safety evaluation of the device. For AEs that are unresolved/ ongoing at time of subject exit from study, any additional information received at follow-up should be documented in the eCRFs up to study completion (i.e., database lock).

Any additional data received up to 3 months after subject discontinuation or exit must be documented and available upon the study sponsor's request. All complaints received after this time period will be considered and processed as spontaneous (following the post-market vigilance procedures) and should be communicated to the medical device's manufacturer as per local requirements.

[figure not shown]
The investigator should also report complaints on non-Alcon products directly to the manufacturer as per the manufacturer's instructions or local regulatory requirements.

11.7 Pregnancy in the Clinical Study

Pregnancy is excluded at the time of enrollment for this study. However, if a subject becomes pregnant during study participation, it will be documented on the source. Pregnancy is not reportable as an AE; however, complications may be reportable and will be decided on a case-by-case basis.

12 ANALYSIS PLAN

Continuous variables will be summarized using the number of observations, mean, SD, median, minimum, and maximum. Categorical variables will be summarized with frequencies and percentages from each category.

Any deviations to the analysis plan will be updated during the course of the study as part of a protocol amendment or will be detailed in the clinical study report.

12.1 Subject Evaluability

Final subject evaluability must be determined prior to breaking the code for masked treatment (lens) sequence assignment and locking the database, based upon the Deviations and Evaluability Plan.

12.2 Analysis Sets

12.2.1 Safety Analysis Set

Safety analyses will be conducted using the safety analysis set on a treatment-emergent basis. As such, the safety analysis set will include all subjects/eyes exposed to any study lenses evaluated in this study, [REDACTED]. For treatment-emergent safety analyses, subjects/eyes will be categorized under the actual study lenses exposed in the corresponding lens sequence.

12.3 Demographic and Baseline Characteristics

Demographic and baseline characteristics will be summarized by lens sequence and overall. Frequencies and percentages will be presented for categorical variables such as sex, age group, and race. Number of observations, mean, SD, median, minimum, and maximum will be presented for continuous variables such as age.

12.4 Effectiveness Analyses

This study defines one primary endpoint [REDACTED]. The Safety Analysis Set will be used [REDACTED].

12.4.1 Analysis of Primary Effectiveness Endpoint(s)

[figure not shown]
The primary objective of this study is to evaluate the VA of the TOTAL30 soft contact lens and the AOHP soft contact lens. The primary endpoint is distance VA with study lenses, collected for each eye in logMAR.

12.4.1.1 Statistical Hypotheses

No inferences are to be made on the primary effectiveness endpoint; therefore, no hypotheses are formulated.

12.4.1.2 Analysis Methods

Descriptive statistics used for continuous variables will be presented.

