Key inclusion criteria (See Section 8.1 for a complete list of inclusion criteria)	
• Current wearers of any commercial spherical soft contact lenses with at least 3 months wearing experience, who would be willing to wear the study lenses for a minimum wearing time of 5 days per week and 8 hours per day.• Able to wear contact lenses within a range of sphere power from -1.00 D to -6.00 D (0.25 D steps) and subject willing and able to wear the study lenses for the full duration of the study.• Willing to NOT use rewetting/lubricating drops at any time during the study.
Key exclusion criteria (See Section 8.2 for a complete list of exclusion criteria)	
• Participation of the subject in a clinical trial within the previous 14 days or currently enrolled in any clinical trial.• Habitual AOHP contact lens wearers (in the past 3 months)• Monovision wear during the study.
Data analysis and sample size justification	Planned Analysis To address the primary objective, descriptive statistics (number of observations, mean, standard deviation, median, minimum, maximum) for visual acuity, collected for each eye, on the logMAR scale will be provided. No inferential testing will be conducted.

	
Sample Size Justification
 
Given the feasibility nature of this study, sample size calculation is not relevant.

Associated materials
	
AOSEPT PLUS with HydraGlyde Cleaning & Disinfecting Solution will be used for daily cleaning and disinfection.
 
Lubrication/rewetting drops will not be permitted during this study.

Table 3–1 Schedule of Study Procedures and Assessments

Procedure/ Assessment	Pre-screening	LENS PAIR 1		LENS PAIR 2		Early Exit	USV
		Visit 1 Screen/Baseline/ Dispense Pair 1	Visit 2 Follow-up Pair 1 [§] / Dispense Pair 2	Visit 3 Follow-up Pair 2 [§] /Exit			
		Visit Window ^Ω		Visit Window ^Ω			
		Day 1	AOHP = [Day 14 (-3/+7 days)] TOTAL30 = [Day 28 (-3/+7 days)]	AOHP = [Day 14 (-3/+7 days)] TOTAL30 = [Day 28 (-3/+7 days)]			
Pre-Screening Consent	X						
Informed Consent		X					
Demographics		X					
Medical History*		X	X		X	X	X
Pregnancy Form*			(X)		(X)	(X)	X
Concomitant Medications*		X	X		X	X	X
Inclusion/Exclusion		X					
Habitual (lens brand, lens power*, lens care)		X					
Keratometry readings (OD, OS)		X					
Manifest refraction*		X	(X)		(X)	(X)	(X)
BCVA* (OD, OS, logMAR distance with manifest refraction)		X	(X)		(X)	(X)	(X)
Biomicroscopy		X	X		X	X	(X)

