Randomization		X					
VA w/ study lenses, (OD, OS, logMAR distance)		X (optimization and baseline measurements for both study lens types)	X (lens pair 1)		X (lens pair 2)	X	X
Slit-lamp photo/video of study lenses*		(X)	(X)		(X)	(X)	(X)
Dispense (provide) study lenses		X					(X)

Procedure/ Assessment	Pre-screening	LENS PAIR 1		LENS PAIR 2		Early Exit	USV
		Visit 1 Screen/Baseline/ Dispense Pair 1	Visit 2 Follow-up Pair 1 ^S / Dispense Pair 2	Visit 3 Follow-up Pair 2 ^S /Exit			
		Visit Window ^Ω		Visit Window ^Ω			
		Day 1	AOHP = [Day 14 (-3/+7 days)] TOTAL30 = [Day 28 (-3/+7 days)]	AOHP = [Day 14 (-3/+7 days)] TOTAL30 = [Day 28 (-3/+7 days)]			
Subjective VAS questionnaire		X (baseline measurements for both study lens)	X (lens pair 1)	X (lens pair 2)		X	(X)

AEs		X	X	X	X	X
Device deficiencies		X	X	X	X	X
Exit Form		(X)	(X)	X	X	(X)

(X) Assessment performed as necessary, eg, decrease of VA by 2 lines or more with investigational product (IP)

USV = Unscheduled Visit

* Source only

^S Subjects are required to wear the study lenses at least 6 hrs on the day of follow-up visits prior to the visit. Follow-up visit time to be within ±2 hours of baseline visit time.

^Ω Visit 2 and 3 visit window and exposure period is dependent on the randomized treatment sequence. AOHP exposure period is to be 14 days (-3/+7 days) and TOTAL30 exposure period is to be 28 days (-3/+7 days)

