5.2 Purpose of the Study

The purpose of this study is to assess the clinical performance of the TOTAL30 contact lens compared to AOHP. The primary endpoint was selected to address the primary objective of the study. Procedures for measurement of these endpoints were selected based on common practice for these assessments and some novel assessment techniques. The design of this study is justified based upon preclinical and clinical testing, as described within the IFU.

AOHP contact lenses were chosen as the comparator product because both of these lenses have a frequent replacement schedule.

[REDACTED]

[REDACTED]

At the end of the study, a clinical study report [REDACTED] will be prepared in accordance with applicable regulatory requirements and standards. [REDACTED]

[REDACTED]

Alcon reserves the right of prior review of any publication or presentation of information related to the study. [REDACTED]

[REDACTED]

[REDACTED]

[REDACTED]

[REDACTED]

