7.2 Rationale for Study Design

This study design is justified based upon an evaluation of the results of relevant preclinical and clinical testing, as described within the IFU.

The crossover design will ensure that the same subject is exposed to both the test and comparator lens materials [REDACTED]

[REDACTED]. The study will include only those subjects who are current wearers of spherical soft contact lenses in both eyes with at least 3 months wearing experience, with a minimum wearing time of 5 days per week and 8 hours per day. [REDACTED]

Furthermore, the subjects will not be permitted to use lubrication/rewetting drops during the duration of the study as this may confound the primary effectiveness endpoint. The study will exclude any habitual AOHP contact lens wearers in the past 3 months prior to consent in order to reduce potential bias of wearers to their habitual contact lenses. The study will also exclude subjects who wish to wear their contact lenses in monovision modality during the study.

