4 EFFECTIVENESS ANALYSIS STRATEGY

This study defines one primary endpoint

will use the Safety Analysis Set.

Continuous variables will be summarized using the number of observations, mean, standard deviation, median, minimum, and maximum. Categorical variables will be summarized with frequencies and percentages from each category.

All data obtained in evaluable participants/eyes will be included in the analysis. No imputation for missing values will be carried out.

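### Does the plan fail its crossover design because the readable text names no within-subject TOTAL30 minus AOHP summary of visual acuity?

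*Protocol*

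**What the plan says.** Protocol 12.4.1 defines the endpoint: "The primary endpoint is distance VA with study lenses, collected for each eye in logMAR". Section 12.4.1.2 gives the method in one sentence: "Descriptive statistics used for continuous variables will be presented". The Planned Analysis in the Protocol Summary promises "descriptive statistics (number of observations, mean, standard deviation, median, minimum, maximum) for visual acuity, collected for each eye". The opening of Protocol 12 sets the general rule: "Continuous variables will be summarized using the number of observations, mean, SD, median, minimum, and maximum". SAP 4 repeats it: "Continuous variables will be summarized using the number of observations, mean, standard deviation, median, minimum, and maximum".

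On design and aim, Protocol 7.2 says: "The crossover design will ensure that the same subject is exposed to both the test and comparator lens materials". Protocol 5.2 says: "The purpose of this study is to assess the clinical performance of the TOTAL30 contact lens compared to AOHP". The VA row of Table 3-1 shows that Visit 1 includes "optimization and baseline measurements for both study lens types", and each lens is measured again at the end of its own wear period.

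The primary objective is narrower than the general purpose. Protocol 6.1 and SAP 1.1 ask for an evaluation of VA with the one lens and with the other. Protocol 12.4.1.1 and SAP 4.2 rule out inference on this endpoint, the SAP Executive Summary sets no decision criteria, and Protocol 12.7 and SAP 7 call the study a feasibility study and give no sample size calculation.

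**The concern.** The main reason to run a crossover is that each subject serves as their own control. If VA is reported only as two lens columns, the reader sees how VA varies between subjects under each lens, but not how much it differs between lenses in the same eye. Two lenses with equal mean VA could agree in every eye, or differ widely in opposite directions, and the columns would look alike.

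There is also a question of who is in each column. The effectiveness analysis uses the Safety Analysis Set, which takes in subjects exposed to any study lens, and missing values are not imputed. A subject with follow-up VA for one lens only could then enter one column and not the other, so the difference of the lens means need not equal the mean paired difference. For a study whose stated purpose is comparative, both points would matter if a comparison of VA were the deliverable and the plan had left it out.

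**Working it through.** The plan gives no SD, correlation, alpha, power or margin, so there is no figure of its own to reproduce. The only numbers are about 36 consented and 32 planned completers (Protocol Summary and Protocol 8). Other values below are marked as assumptions.

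**1. Is the summary absent from the plan?** The SAP contents list 4.3 (statistical methods for effectiveness) and 4.3.1 (primary effectiveness analyses). The SAP body as published goes from 4.2 straight to 4.6. The Protocol contents have a gap between 12.4.1.1 and 12.5, and Protocol 12.4 has blacked-out text just after it mentions the primary endpoint. The section where a lens difference would most naturally be specified cannot be read. Text missing for that reason does not count as missing from the plan.

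**2. Does the readable text exclude it?** No. The general rule in Protocol 12 and SAP 4 covers any continuous variable. A within-eye difference in logMAR is a derived continuous variable and can be summarised under that rule without contradicting anything.

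**3. What do the lens columns give and withhold?** With complete pairs, the mean of the differences equals the difference of the means, so the central comparative figure can be read from the columns. The spread cannot. Per eye,

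SD of difference = √(s₁² + s₂² − 2ρs₁s₂), which for s₁ = s₂ = s is s√(2(1 − ρ)).

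| assumed ρ | 0.5 | 0.6 | 0.7 | 0.8 |
|---|---|---|---|---|
| SD of difference | 1.00s | 0.89s | 0.77s | 0.63s |

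With s₂ = 1.25s₁ it is 1.146s₁ at ρ = 0.5 and 0.750s₁ at ρ = 0.8. With ρ unknown, the columns bound it only between |s₁ − s₂| and s₁ + s₂, that is 0 to 2s for equal SDs. This part of the worry is arithmetically right.

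**4. How much could incomplete pairs matter?** If k subjects have follow-up VA for one lens only and c subjects have both, that lens mean moves by k/(c + k) times the amount d by which the k subjects differ from the c.

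- c = 32, k = 4 (36 − 32): 4/36 = 0.11.
- c = 28, k = 8 (assumed, because 32 is a target): 8/36 = 0.22.

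So 0.11 is not a ceiling; it holds only if 32 complete and no more than 36 consent. The value of d is unknown. At an assumed d of 0.10 logMAR the shifts would be 0.011 and 0.022 logMAR. They may be zero, since the 36 includes screen failures, and evaluability rules and VA taken at an Early Exit visit also decide who is counted.

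**5. What would the paired follow-up difference measure?** Protocol 7.3 places follow-up at Day 28 for TOTAL30 and Day 14 for AOHP, and Protocol 10 gives windows of Days 25–35 and 11–21. Protocol 7.1 allows power to be optimised per lens type, with the two dispensed lenses up to 0.25 D apart. The difference would therefore mix lens, wear time and fitted power. The Visit 1 difference is free of the wear-time mismatch but still includes fitting.

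**6. What depends on it?** Nothing stated in the plan. There is no hypothesis, threshold, success rule or sample size tied to a lens difference, and the stated primary objective is met by one summary per lens and eye.

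**The case for a change.** The strongest opposing case is this. The sentence in Protocol 12.4.1.2 has no redaction mark, and the Planned Analysis in the Protocol Summary states how the primary objective will be addressed. Neither mentions a difference. The purpose is comparative, the pairs are collected by design, and the SD, median and extremes of the paired difference cannot be rebuilt from the columns. A descriptive table would need no test and no extra subject, visit or measurement.

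The algebra stands, and so does the point that such a table would be informative. Three things do not follow.

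- The comparative wording in Protocol 5.2 concerns clinical performance overall, and the Protocol Summary frames the aim as description. Side-by-side columns do that. Other objectives and endpoints are blacked out, Protocol 10.2.7 refers to further effectiveness assessments, and Table 3-1 schedules a subjective questionnaire for both lenses. That VA is the only effectiveness endpoint one can read is partly an effect of redaction.
- An unredacted sentence in the Protocol does not show that the SAP is silent, because SAP 4.3.1 cannot be read.
- The addition is cheap but not wholly free. Under Protocol 4 a change to the Protocol text needs an amendment, unless it is only logistical or administrative. A full version by eye, time point (Visit 1 and follow-up) and grouping (each sequence and overall) would hold 2 × 2 × 3 × 6 = 72 figures. Protocol 12 also lets departures from the analysis plan be described in the study report, so a paired summary could be reported without editing the Protocol.

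**Conclusion.** The concern does not hold. Carried out as written, the plan gives valid descriptive results for the primary objective it states, and it draws no inference that would need the pairing. The claim of an omission cannot be established, because the SAP section on the primary analysis is not in the public text, and the readable text leaves room for a paired summary.

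What a reader of lens columns alone would lack is the spread of the within-eye difference: 0.63 to 1.00 times the lens SD for assumed correlations of 0.8 down to 0.5, with equal lens SDs. With complete pairs the mean difference is not lost. With incomplete pairs the weight of one-lens subjects is 0.11 at the planned numbers and 0.22 in the less favourable assumed case, applied to a difference that the documents do not give. None of this alters a stated result, decision or conclusion. Whether to print a paired table is a matter of reporting preference.
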